4.3.1 Marqibo®

4.3.1.1 Weekly assessment of neurologic function should be performed prior to administration of Marqibo®. (Appendix 4).

- Subjects who develop grade 3 or greater sensory or motor neuropathy will discontinue Marqibo® treatment.
- Subjects with < grade 3 neuropathy will be closely monitored without any adjustment to Marqibo® dose

4.3.1.2 Dosing will NOT be held for cytopenias.

4.3.1.3 Transaminase elevation: Marqibo® dosing will be delayed for grade 3 or higher AST (aspartate aminotransferase) or ALT (alanine aminotransferase) elevation

until resolution to grade 2 or baseline, then resume full dose. Maximum allowable delays are specified in section 4.3.

4.3.1.4 Hyperbilirubinemia:

Bilirubin Level	Dose Delay
Total bilirubin < 1.5 x upper limit of normal and direct bilirubin < 1.4 mg/dL	None, administer full dose
Total bilirubin > 1.5 x upper limit of normal, and/or direct bilirubin \geq 1.4 mg/dL	Withhold dose until resolution to grade 1 bilirubin or baseline and direct bilirubin < 1.4, then resume full dose. Maximum allowable delays are specified in section 4.3.

For subjects with documented Gilbert's disease, no modification is necessary unless the total bilirubin exceeds 5 x ULN or the direct bilirubin is \geq 1.4 mg/dL.

4.3.1.5 Jaw Pain: Treat with analgesics; do not modify Marqibo® dose.

4.3.1.6 Extravasation: In the event of an extravasation, discontinue the IV administration of the drug and institute appropriate measures according to institutional guidelines.

4.3.1.7 Drug Interactions: See Section 4.4

4.3.2 Pegaspargase

4.3.2.1 Allergic Reactions

Local Reactions (inflammation at injection site, swelling): Continue pegaspargase administration in the presence of Grade 1 allergy (transient flushing or rash; drug fever < 38°C).

Anaphylaxis/Systemic Allergic reactions: Systemic allergy is associated with the presence of pegaspargase neutralizing antibodies, which render asparaginase therapy ineffective. Discontinue if the patient develops a systemic allergic reaction (urticaria, wheezing, laryngospasm, hypotension, etc).

4.3.2.2 Coagulopathy: If symptomatic, hold pegaspargase until symptoms resolve, allowing for up to a one-week delay in scheduled dosing or resume with the next scheduled dose. Consider factor replacement (FFP, cryoprecipitate, factor

VIIa). Do not withhold dose for abnormal laboratory findings without clinical symptoms.

4.3.2.3 Hyperbilirubinemia: Pegaspargase should be held in patients with an elevated direct bilirubin ≥ 1.4 mg/dL. Resume when direct bilirubin < 1.4 mg/dL, may give within one week of scheduled dosing.

Direct Bili	Dose modification
≤ 3 mg/dL	Full dose
3.1-5 mg/dL	Hold asparaginase and result when direct bilirubin ≤ 2 mg/dL
>5 mg/dL	HOLD asparaginase; do not substitute other asparaginase products; do not make up missed doses

4.3.2.4 Hyperglycemia: Do not modify dose. Treat hyperglycemia as medically indicated.

4.3.2.5 Hyperlipidemia: Do not modify dose.

4.3.2.6 Ketoacidosis: Hold pegaspargase until blood glucose can be regulated with insulin.

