4.1 Treatment Course

Only 1 course of treatment will be permitted. Upon completion of treatment on this study, plans for additional therapy will be at the discretion of the treating team.

As of Amendment 3, cohorts A and B will be treating at dose level 1; Cohort C will be treating at dose level 2.

Marqibo Dose Levels

Dose Level 1: 1.5 mg/m²

Dose Level 2: 2.0 mg/m²

Cohort A:

	Day 1	Day 2	Day 3	Day 4	Day 5	Day 8	Day 15	Day 16	Day 17	Day 18	Day 19	Day 22	Day 29
Marqibo®	●					●	●					●	Response Evaluator
Dexamethasone	●	●	●	●	●		●	●	●	●	●		
Mitoxantrone	●	●											
Pegaspargase#			●						●				
IT Methotrexate	●					●							

asparaginase Erwinia chrysanthemi (Erwinaze®), crisantapase (Erwinase®) asparaginase Erwinia chrysanthemi (recombinant)-rywn (Rylaze®) may be substituted for allergy to Pegaspargase. See below.

Drug Administration Order

Marqibo will be administered first. Mitoxantrone will follow Marqibo administration on day 1 with dexrazoxane to be given immediately before mitoxantrone (when dexrazoxane is utilized [optional]). Timing of IT methotrexate is flexible in regards to the timing of Marqibo, but should not be given simultaneously in order to reduce the risk of administration route error.

Marqibo® (Dose level 1 only as of Amendment 3)

- Dose Level 1: 1.5 mg/m²/dose (no dose cap) given IV over 60 minutes (±10 minutes) on days 1, 8, 15 and 22.
- ~~Dose Level 2: 2 mg/m²/dose (no dose cap) given IV over 60 minutes (±10 minutes) on days 1, 8, 15 and 22.~~
- Review list of concomitant medications that are prohibited (CYP3A4 inhibitors) or to be used with caution (Appendix 3). See section 4.5 for drug interactions.
- Dose will be given over 60 minutes ± 10 minutes

Dexamethasone

- 20 mg/m²/day divided BID given orally on days 1 through 5 and 15 through 19. The two doses should be separated by at least 8 hours
- Any oral formulation of dexamethasone is acceptable
- IV may be given if oral formulation is not tolerated (please document reason or al could not be given)

Mitoxantrone

- 10 mg/m²/day given on days 1 and 2 as a short IV infusion over 5-15 minutes. Do not infuse over less than 3 minutes.
- Dose will be given over 5-15 minutes
- See section 5.6 for guidance on optional cardioprotection.

Pegaspargase

- 2,500 international units/m²/day IM or IV on days 3 and 17. **(Cap individual dose at 3,750 IU, based on vial size)**

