4.3 Dose Delays and Modifications

The intent of this study design is for all patients to receive and complete one course of therapy. Patients who exhibit signs of disease progression or experience an unacceptable toxicity will be discontinued from treatment. For Marqibo® dosing delays due to hepatotoxicity (see sections 4.3.1.3 and 4.3.1.4), a maximum delay of 7 days is allowed per dose and no dosing is permitted beyond day 35. There will be no dose delays or dose reductions of study drugs for hematologic toxicity during therapy. At the time that interim analysis is performed to evaluate toxicity (see sections 9.2 - 9.5), if it is determined that the regimen has excessive toxicity, protocol amendment may be considered to modify the dose of Marqibo®.

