9.1 Endpoints

9.1.1 Primary Endpoint

Cohort A

The primary endpoint in Cohort A is whether a patient is successfully treated with UK ALL R3/Marqibo® at nearly full dose without inordinate delays in the resolution of hematologic and non-hematologic toxicity that preclude timely continuation with subsequent treatment.

Specifically, a patient will be considered successfully treated if:

- a. The patient has received 16 of 20 prescribed doses of Dexamethasone, 2 of 2 prescribed doses of Mitoxantrone, 3 of 4 prescribed doses of Marqibo®, and 1 of 2 doses of pegaspargase.
- b. The patient has not experienced a dose limiting toxicity (DLT) as defined in section 4.2.

A patient will be considered NOT successfully treated if (s)he has experienced a dose limiting toxicity (DLT) as defined in section 4.2, or has received fewer than the minimum numbers of prescribed doses as described in (a) above for reasons not unequivocally unrelated to treatment toxicity (see section 9.3.1)

Cohort B

The primary endpoint in Cohort B is whether a patient is successfully treated with UK ALL R3/Marqibo® without mitoxantrone at nearly full dose without inordinate delays in the resolution of hematologic and non-hematologic toxicity that preclude timely continuation with subsequent treatment.

Specifically, a patient will be considered successfully treated if:

- a. The patient has received 16 of 20 prescribed doses of Dexamethasone, 3 of 4 prescribed doses of Marqibo® and 1 of 2 doses of pegaspargase.
- b. The patient has not experienced a dose limiting toxicity (DLT) as defined in section 4.2

A patient will be considered NOT successfully treated if (s)he has experienced a dose limiting toxicity (DLT) as defined in section 4.2, or has received fewer than the minimum numbers of prescribed doses as described in (a) above for reasons not unequivocally unrelated to treatment toxicity (see section 9.3.1)

Cohort C

The primary endpoint in Cohort C is whether a patient is successfully treated with one cycle (14 days) of the modified maintenance treatment at nearly full dose without inordinate delays in the resolution of non-hematologic toxicity that preclude timely continuation with subsequent treatment.

Specifically, a patient will be considered successfully treated if during the first course of modified maintenance treatment:

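### Section 4.3.2.3 tells sites both to hold pegaspargase and to give it at full dose when direct bilirubin is 1.4 to 3.0 mg/dL, and no rule says which applies (Cohorts A and B)

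*Combined protocol and SAP*

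**What the plan says.** Pegaspargase is given in Cohorts A and B only, at 2,500 "international units/m²/day IM or IV on days 3 and 17" (4.1), with each dose capped at 3,750 IU. Section 4.3.2.3 then gives two sets of instructions for high direct bilirubin.

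- **Sentence.** "Pegaspargase should be held in patients with an elevated direct bilirubin ≥ 1.4 mg/dL". It continues: "Resume when direct bilirubin < 1.4 mg/dL, may give within one week of scheduled dosing".
- **Table, directly beneath.** Full dose at 3 mg/dL or below. At 3.1 to 5 mg/dL: "Hold asparaginase and result when direct bilirubin ≤ 2 mg/dL". Above 5 mg/dL: "HOLD asparaginase; do not substitute other asparaginase products; do not make up missed doses".

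For Marqibo, 4.3.1.4 withholds the dose when direct bilirubin is 1.4 mg/dL or more (or total bilirubin exceeds 1.5 × ULN): "Withhold dose until resolution to grade 1 bilirubin or baseline and direct bilirubin < 1.4, then resume full dose". Section 4.3 limits Marqibo delays for hepatotoxicity: "a maximum delay of 7 days is allowed per dose and no dosing is permitted beyond day 35".

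The dose minimum for treatment success in 9.1.1 includes, for Cohort A, "3 of 4 prescribed doses of Marqibo®, and 1 of 2 doses of pegaspargase". Cohort B has the same minimum for these two drugs.

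**The concern.** A site with a patient at, say, 2.0 mg/dL on day 17 departs from one instruction whatever it does. Neither rule is limited to a cohort, a dose number or a product. The table's last row forbids switching to other asparaginase products, so the table cannot be read as a separate rule for Erwinia preparations. Sections 4.1, 4.3, 6.5 and 9.1.1 set no precedence.

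Sites will see such values if they occur. Direct bilirubin is in the chemistry panel of 7.1, drawn twice weekly and within one day before Marqibo doses 2, 3 and 4. The sample before dose 3 therefore comes shortly before the day 17 pegaspargase dose. Under the table, a patient whose day 15 Marqibo is on hold for a direct bilirubin in this band would still receive full-dose pegaspargase two days later.

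The main stake is patient safety. Section 2.2 warns that hepatotoxicity may increase when Marqibo is combined with other hepatotoxic agents. Section 6.5.2 lists abnormal liver function tests (occasional) and liver failure (rare) for pegaspargase.

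A second stake is interpretation. Non-hematologic DLTs are attributed to the whole regimen (4.2.1.1), and the dose decisions in 9.2 rest on the first six evaluable patients per cohort and dose level. Pegaspargase dosing that differs between sites during liver injury could blur the reading of hepatic DLTs. The documents give nothing from which to quantify this.

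**Working it through.** There is no planned figure to reproduce. The check sets the two rules side by side and then asks what the difference does to doses and to the endpoint.

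**1. The two rules by direct bilirubin (mg/dL)**

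| Direct bilirubin | Sentence | Table |
|---|---|---|
| below 1.4 | give | full dose |
| 1.4 to 3.0 | hold | full dose |
| 3.1 to 5 | hold; restart below 1.4 | hold; restart at 2 or lower |
| above 5 | hold; may give within one week | hold; no make-up |

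In steps of 0.1, the instructions conflict at all 17 values from 1.4 to 3.0. They agree on giving below 1.4 and on holding from 3.1 upward. After a value of 3.1 to 5, the restart thresholds conflict from 1.4 to 2.0. The hold thresholds differ by 3.0 / 1.4 = 2.14.

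**2. Inputs for the dose counts**

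- Marqibo is due on days 1, 8, 15 and 22 (4.1). It is withheld at 1.4 or more (4.3.1.4) and may be up to 7 days late (4.3), so the windows for doses 2 to 4 are days 8–15, 15–22 and 22–29.
- Pegaspargase is due on days 3 and 17. Under the sentence it can be given on days 3–10 or 17–24 once the value is below 1.4. Under the table it is always given on schedule at 3.0 or below.
- Assumptions: bilirubin is known daily, day 1 Marqibo is given, and total bilirubin does not hold Marqibo separately. If it did, changes in success status would be rarer still.

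**3. Worked patterns, with direct bilirubin in the 1.4–3.0 band on the days shown**

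| Days in band | Marqibo | Pegaspargase, sentence | Pegaspargase, table | Dose minimum |
|---|---|---|---|---|
| 17–24 | 4 of 4 (day 22 dose on day 25) | 1 of 2 | 2 of 2 | met under both |
| 3–24 | 2 of 4 | 0 of 2 | 2 of 2 | missed under both |
| 3–10 and 17–24 | 4 of 4 (days 1, 11, 15, 25) | 0 of 2 | 2 of 2 | missed under the sentence, met under the table |

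In the first pattern the totals are 1 × 2,500 = 2,500 IU/m² and 2 × 2,500 = 5,000 IU/m², subject to the cap per dose.

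**4. All single continuous elevations starting and ending within days 2–29**

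- Number of intervals: 28 × 29 / 2 = 406.
- First pegaspargase dose lost under the sentence (start by day 3, end on day 10 or later): 2 × 20 = 40.
- Second dose lost (start by day 17, end on day 24 or later): 16 × 6 = 96.
- Both lost (start by day 3, end on day 24 or later): 2 × 6 = 12.
- At least one lost: 40 + 96 − 12 = 124.

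Because 1 of 2 pegaspargase doses is enough, only the 12 intervals that lose both doses could change success status. In all 12, the windows for Marqibo doses 2 and 3 lie wholly inside the elevation, so at most 2 of 4 Marqibo doses are given. The 3-of-4 minimum is then missed under either rule, and success status changes in 0 of 406.

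A change needs two separate elevations, covering days 3–10 and days 17–24 in full, with at least one day below 1.4 during days 11–16. The third pattern in step 3 is an example. These are counts of possible patterns, not probabilities, and the documents give no frequency for them.

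**The case against.** The strongest reply is about weight. The endpoint is hardly affected, entry requires total bilirubin of at most 1.5 × ULN (3.3.5), and so in practice mainly the day 17 dose of a background drug is exposed. All of that stands.

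The safety case can also be called selective. Section 2.2 goes on to promise daily monitoring, 7.1 schedules chemistries twice weekly, and 12.2 provides weekly safety review as needed. Liver failure is listed as rare. The elective de-escalation of Cohort B (9.2) cited known Marqibo hepatic toxicity, one hepatic DLT and one near-DLT, and did not mention pegaspargase. These points are correct and limit what can be claimed. But monitoring only shows the site the bilirubin value; it does not say what to do with it.

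The match with the Marqibo threshold does not prove which rule was meant. The protocol sets bilirubin limits drug by drug: mitoxantrone, for example, is given at full dose below a total bilirubin of 5.0 mg/dL (4.3.5.1). Section 6.5.1 states that pegaspargase half-life does not depend on hepatic function. A more permissive pegaspargase rule is therefore defensible, and the choice is a clinical one.

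The make-up point is partly reconcilable, since the table's bar on making up doses above 5 mg/dL could be read as an exception to the sentence's general one-week allowance. The hold and restart thresholds cannot be reconciled that way.

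Finally, one of the two rules may be left over from a revision. Struck-through text is visible in 4.1, but none is marked on either rule here. Sections 2.4.1 and 2.4.2 were not in the text reviewed; section 4.0 describes them as a review of experience to date.

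**Conclusion.** The concern holds. As written, 4.3.2.3 gives incompatible instructions for pegaspargase across the whole band from 1.4 to 3.0 mg/dL in Cohorts A and B, with a second conflict over restart. No precedence is stated in the text reviewed.

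The consequence for a patient can be one full dose of pegaspargase given or omitted while direct biliribin is raised, with either action following some protocol text. The effect on the primary endpoint through dose counts is small under the assumptions in the working. The reason to correct it is a contradictory dosing rule for a hepatotoxic drug in young patients, and dosing that may differ between sites. How often patients will fall in the band cannot be estimated from the documents, and the conclusion does not depend on it.

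**What to change.** Keep one rule in 4.3.2.3. The clinical team should choose between two options.

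- **Delete the table.** Pegaspargase is held at direct bilirubin of 1.4 mg/dL or more and resumed below 1.4, within one week of schedule. This matches 4.3.1.4. The price is that more asparaginase is delayed or omitted.
- **Delete the sentence.** The table governs. In its second row, *result* should be replaced by the intended restart instruction, and the section should state that pegaspargase may be given while Marqibo is on hold. The price is that asparaginase is given at bilirubin levels where Marqibo is withheld.

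Either option removes one short block of text (the hold-and-resume instruction or a three-row table) by amendment, with notice to sites. It adds no procedures, visits or patients.

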4.3.2.7 Pancreatitis

Grade 2 (Enzyme elevation or radiologic findings only) Hold until symptoms and signs subside, and enzyme levels return to normal and then resume at full dose, allowing for up to a one-week delay from scheduled dosing

Grade 3-4 Asparaginase should be permanently discontinued. elevation ($> 2.0x$ ULN). Severe pancreatitis is a contraindication to additional asparaginase administration.

4.3.2.8 Thrombosis (excluding minor central venous catheter tip related): Withhold pegaspargase and treat with appropriate anticoagulant and/or antithrombotic therapy, as indicated. Upon resolution of symptoms consider resuming asparaginase, while continuing anticoagulant and/or antithrombotic therapy, may allow for up to a one-week delay from scheduled dosing. Do not withhold dose for abnormal laboratory findings without clinical sequelae. Consider evaluation for inherited predisposition to thrombosis.

4.3.2.9 CNS Events (bleed, thrombosis or infarction): Hold pegaspargase. Treat with FFP, factors or anticoagulation as appropriate. Resume at full dose when all

symptoms have resolved (and evidence of recanalization in case of thrombosis by CT/MRI). May allow for up to a one-week delay from scheduled dosing. Consider evaluation for inherited predisposition to thrombosis.

4.3.3 Intrathecal Methotrexate

4.3.3.1 Systemic toxicity: The dosage for IT methotrexate will not be reduced for systemic toxicity (myelosuppression, mucositis, etc.). Instead, leucovorin may be used at a dose of 5 mg/m²/dose every 12 hours x 2 doses, beginning 48 hours after the IT therapy has been delivered. This may reduce the risk of worsening myelosuppression or mucositis. Leucovorin may also be used in subjects with hepatic transaminase elevation to reduce risk of worsening hepatotoxicity from IT methotrexate.

4.3.3.2 Dose modifications following an episode of acute neurotoxicity: The treating physician must evaluate the patient and, with the family, make the best possible decision with respect to the relative risk and benefit of continued therapy.

4.3.3.3 Hydrocephalus, microcephaly or known abnormality of CSF flow precluding intrathecal chemotherapy via lumbar puncture: Intraventricular chemotherapy via Ommaya catheter may be used in place of intrathecal therapy delivered by LP. Intraventricular chemotherapy should be given according to the same schedule, but at **50% of the corresponding age-based doses** that would be given by LP. NOTE: Obstruction to CSF flow may be a contraindication to intrathecal and/or intraventricular therapy.

4.3.3.4 Viral, bacterial, or fungal meningitis: Omit until resolved.

4.3.4 Dexamethasone

4.3.4.1 Hypertension: Dose should not be reduced. Sodium restriction and antihypertensives should be employed in an effort to control hypertension. Avoid calcium channel blockers due to their potential prohemorrhagic effect.

4.3.4.2 Hyperglycemia: Do not modify dose. Treat hyperglycemia as medically indicated.

4.3.4.3 Pancreatitis: Do not modify dose for asymptomatic elevations of amylase and/or lipase. Discontinue steroids, except for stress doses, in the presence of hemorrhagic pancreatitis or severe pancreatitis (abdominal pain > 72 hours and > Grade 3 amylase elevation (> 2.0x ULN)). Steroids may resume with resolution of pancreatitis, as defined by amylase and lipase to baseline or ≤ grade 1 and resolution of pain.

4.3.4.4 Osteonecrosis: Do not modify corticosteroid therapy for osteonecrosis.

4.3.4.5 Severe infection: Do not hold or discontinue steroids without contacting the study chair or vice chair.

4.3.4.6 Severe psychosis: Steroid dose may be reduced by 50%.

4.3.5 Mitoxantrone

4.3.5.1 Hyperbilirubinemia

Total Bilirubin	Dose Reduction
< 5.0 mg/dL	Full dose
≥ 5.0 mg/dL	Withhold dose and administer next scheduled dose if toxicity has resolved. Do not make up missed doses.

4.4 Concurrent Therapy and Drug Interactions

Anti-Cancer Therapy: Concurrent anti-cancer therapy not defined within this protocol, including chemotherapy, radiation therapy, immunotherapy, or biologic therapy may NOT be administered to patients receiving study drug. If these treatments are administered the patient will be removed from protocol therapy.

Investigational Agents: No other investigational agents may be given while the patient is on protocol therapy.

Complementary/Alternative Therapies: Use of complementary/alternative therapies is not specifically prohibited, but is discouraged. All therapies should be reviewed with the study team for the potential of drug interactions with Marqibo® or any of the other chemotherapeutic agents.

Allopurinol: Tumor lysis syndrome prophylaxis should be employed for all patients. Allopurinol should ideally be started at a dose of approximately 100 mg/m²/dose PO TID (maximum dose 600 mg/day/subject) at least 8 hours prior to the first dose of chemotherapy and continue until it is apparent that no tumor lysis has developed after 1 week of treatment. Alternatively, rasburicase may be employed as clinically indicated.

Drug Interactions: No formal drug interaction studies have been conducted with Marqibo®. Marqibo® is expected to interact with drugs known to interact with standard formulation vincristine sulfate. Simultaneous oral or intravenous administration of phenytoin and antineoplastic chemotherapy combinations that included non-liposomal vincristine sulfate have been reported to reduce blood levels of phenytoin and to increase seizure activity. Close monitoring is recommended for subjects taking agents with narrow therapeutic indices and metabolized by the

liver, such as warfarin, phenytoin, quinidine, carbamazepine, phenobarbital, cyclosporine and digoxin.

Vincristine sulfate, the active agent in Marqibo®, is a substrate for cytochrome P450 3A isoenzymes (CYP3A); therefore the concomitant use of strong CYP3A inhibitors should be avoided (e.g., ketoconazole, itraconazole, voriconazole, posaconazole, clarithromycin, atazanavir, indinavir, nefazodone, nelfinavir, ritonavir, saquinavir, telithromycin). Concurrent administration of itraconazole with vincristine has shown to increase onset and severity of neuromuscular adverse effects of vincristine. If anti-fungal therapies are required during study treatment, alternative anti-fungals should be evaluated prior to considering any azoles. ***In the event that it is determined that an azole antifungal is required to treat a documented or suspected fungal infection, the decision to initiate therapy should be made after discussion with the Study Chair or Vice Chair.*** If permission is granted for the use of azole therapy, all azole therapy must be held for 24 hours before AND after each dose of Marqibo®.

Similarly, the concomitant use of strong CYP 3A inducers should be avoided (e.g., phenytoin, carbamazepine, rifampin, rifabutin, rifapentin, phenobarbital, St. John's Wort) as these may decrease Marqibo® levels.

Vincristine sulfate is also a substrate for p-glycoprotein (p-gp). The effects of concomitant use of potent p-gp inhibitors or inducers has not been investigated; it is likely that these agents will alter the pharmacokinetics or pharmacodynamics of Marqibo®. Therefore the concomitant use of potent p-gp inhibitors or inducers should be avoided.

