 Mitoxantrone			
Total Cumulative Dose			

APPENDIX 3: PARTIAL LIST OF CONCOMITANT MEDICATIONS KNOWN TO INTERACT WITH CYTOCHROME P450-3A4 ISOENZYMES AND/OR P-GLYCOPROTEIN (TO BE USED WITH CAUTION)

Please note that this is not a comprehensive listing and other medications should be reviewed with the PI.

- Atazanavir
- Atorvastin
- Azithromycin
- Carbamazepine
- Chlorpheniramine
- Cimetidine
- Ciprofloxacin
- Clarithromycin
- **Clotrimazole***
- Cyclosporine
- Dexamethasone[^]
- Digoxin
- Diltiazem
- Ergotamine
- Erythromycin
- **Fluconazole***
- Grapefruit Juice
- Haloperidol
- Indinavir
- **Itraconazole***
- **Ketoconazole***
- Lidocaine
- Lovastatin
- **Miconazole***
- Nefazodone
- Nelfinavir
- Norfloxacin
- Orphenadrine
- Paroxetine
- Phenobarbital
- Phenytoin
- **Posaconazole***
- Progesterone
- Rapamycin
- Rifabutin
- Rifampin
- Rifapentine
- Ritonavir
- Rosiglitazone
- Saquinavir
- Sertraline
- Simvastatin
- St. John's Wort
- Tacrolimus
- Tamoxifen
- Telithromycin
- Toremfina
- Trazadone
- Verapamil
- **Voriconazole***
- Zafirlukast

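### The same CYP3A4 inhibitors and inducers have conflicting statuses in 4.1, 4.4 and Appendix 3, and 4.1 cites a section 4.5 that is not there

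*Combined protocol and SAP*

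**What the plan says.** Four places in the protocol bear on this.

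- **Section 4.1.** The Marqibo instructions for each of the three cohorts contain the bullet "Review list of concomitant medications that are prohibited (CYP3A4 inhibitors) or to be used with caution (Appendix 3". The prohibition is attached to inhibitors; inducers are not named. The same bullet refers the site to section 4.5 for drug interactions.
- **Section 4.4, on Marqibo exposure.** Vincristine is described as a CYP3A substrate, "therefore the concomitant use of strong CYP3A inhibitors should be avoided", with 12 examples. For inducers, "the concomitant use of strong CYP 3A inducers should be avoided (e.g., phenytoin, carbamazepine" opens a list of 7, and the reason given is "as these may decrease Marqibo® levels".
- **Section 4.4, one paragraph earlier.** "Close monitoring is recommended for subjects taking agents with narrow therapeutic indices and metabolized by the", continuing "liver, such as warfarin, phenytoin, quinidine, carbamazepine, phenobarbital, cyclosporine and digoxin".
- **Appendix 3.** The heading describes medications "KNOWN TO INTERACT WITH CYTOCHROME P450-3A4 ISOENZYMES AND/OR P-GLYCOPROTEIN (TO BE USED WITH CAUTION". Below it is one undivided alphabetical list. Azole antifungals are starred as needing approval. The only other footnote explains that dexamethasone, which is on the list, is part of the trial treatment.

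**The concern.** A site that needs to know whether a patient may take one of these drugs gets a different answer from each place it looks. The list it is sent to carries the mildest wording. The protocol itself expects interacting drugs to matter: it says inducers may lower Marqibo levels, and that itraconazole given with vincristine brought on neuromuscular effects earlier and made them worse.

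Two results could be affected. The primary endpoint in 9.1.1 is a tolerability outcome, judged in groups of 6 to 12 evaluable patients per cohort and dose level. The PK analysis in 9.4.4 estimates trough levels, AUC and half-life for comparison with a published adult study and a paediatric Phase I study. Section 9.4.4 has no rule for samples taken while a patient is on an interacting drug.

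**Working it through.** The plan states no figure on this point, so the check compares the passages and counts drugs.

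**Inputs.** The two example lists in 4.4 (12 strong inhibitors and 7 strong inducers), the 4.1 bullet, the close-monitoring sentence in 4.4, and the Appendix 3 list with its footnotes.

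**Status of each drug named in 4.4**

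| Drugs | Number | 4.1 | 4.4 | Appendix 3 |
|---|---|---|---|---|
| Clarithromycin, atazanavir, indinavir, nefazodone, nelfinavir, ritonavir, saquinavir, telithromycin | 8 | prohibited | avoid | caution |
| Rifampin, rifabutin, rifapentine, St. John's Wort | 4 | not named | avoid | caution |
| Phenytoin, carbamazepine, phenobarbital | 3 | not named | avoid, and also close monitoring | caution |
| Ketoconazole, itraconazole, voriconazole, posaconazole | 4 | prohibited | avoid, plus a separate azole rule | caution, with approval |

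**Counts.** 8 + 4 + 3 + 4 = 19, which agrees with 12 + 7. All 19 are in Appendix 3. The 4 azoles are set aside because they have their own provisions (3.4.6, 4.4, 5.2 and the Appendix 3 footnote). That leaves 19 − 4 = 15 drugs with more than one status:

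- 8 inhibitors with three wordings;
- 4 inducers with two;
- 3 inducers with two, plus the monitoring sentence.

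**Practical reach.** Exclusion 3.4.10 bars patients with known HIV. This makes 5 of the 8 inhibitors unlikely on study (atazanavir, indinavir, nelfinavir, ritonavir, saquinavir). That leaves 8 − 5 = 3 inhibitors and 7 inducers, so 10 of the 15. No eligibility criterion names any of those 10.

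**Scope of the prohibition.** 4.1 speaks of CYP3A4 inhibitors without a strength qualifier; 4.4 limits its advice to strong ones. Appendix 3 does not separate inhibitors from inducers or strong from other. It also includes dexamethasone, which every cohort receives, so it cannot serve as a list of prohibited drugs. If the Appendix 3 reference in 4.1 covers only the caution half of the sentence, the protocol has no list headed as prohibited, and the same inhibitors are still in the caution list.

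**Cross-reference.** The contents and the body both end section 4 at 4.4, where the interaction text stands. The reference to 4.5 leads nowhere.

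**Effect of setting PK samples aside.** Section 9.4.4 assumes a trough CV of about 100% and 25 evaluable patients. The relative standard error of the mean is 100%/√25 = 20.0%. The plan prints 17%, although its bound of 40% fits 1.96 × 20.0% = 39.2%; nothing here depends on that difference. The documents do not say how many patients would be on an interacting drug. As an assumption, with 1, 2 or 4 set aside:

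- 100%/√24 = 20.4%
- 100%/√23 = 20.9%
- 100%/√21 = 21.8%

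A second summary without those patients would lose little precision.

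**The case against.** The strongest case on the other side is that this is a matter of drafting. The two 4.4 instructions serve different purposes. The monitoring sentence follows a remark about reduced phenytoin levels and seizures. It applies to drugs with a narrow therapeutic index, including warfarin and digoxin, so it protects the effect of the co-medication. The later sentence protects Marqibo levels. Advice to avoid a drug is not a ban, so a site could avoid these drugs where possible and monitor patients who must stay on them. Section 4.3.1.7 gives the correct reference to 4.4. St. John's Wort also falls under the 4.4 requirement to review complementary therapies with the study team.

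Much of this stands. Four stronger readings that a reader might infer are not supported:

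- *That 4.1 prohibits inducers.* Its parenthesis names inhibitors only.
- *That 4.4 treats monitoring as sufficient for the three anticonvulsants.* The sentence does not say so, and the advice to avoid them follows in the same section.
- *That exposure does differ between sites.* The documents give a direction for inducers, but no effect size and no frequency of use.
- *That dose decisions would be changed.* One patient in six is 16.7 percentage points, but that is true of any patient for any reason. A DLT in a patient on an inhibitor is not misclassified under 9.1.1. Section 9.2 uses both a limit of 2 in 6 and a limit of 1 failure in the first 6, and says the design is not prescriptive. When more than one third fail, the committee reviews the toxicities and could consider a co-medication as the cause.

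The objection does not remove the conflict over inhibitors (prohibited, avoid, caution) or over inducers (avoid, caution). Nor does it say whether a patient already taking phenytoin, carbamazepine or phenobarbital may be treated.

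**Conclusion.** The concern holds as an inconsistency in instructions that sites act on. Fifteen named non-azole drugs have more than one status across 4.1, 4.4 and Appendix 3. Ten of them remain plausible on study once the HIV exclusion is considered. The reference to 4.5 in 4.1 is wrong. Exposure and tolerability could vary with the passage followed, but the size of any effect cannot be estimated from the documents.

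The conclusion rests on reading Appendix 3 as a single list under its heading and on taking the 4.4 examples as they stand. It does not depend on which status is clinically right, and this review takes no position on that. The PK consequence is limited because PK is an exploratory objective (1.2.4, 9.1.2). The correction should be made, but the point does not undermine the design.

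**What to change.** 1. Reconcile 4.1 (all three cohorts), the close-monitoring and avoidance sentences in 4.4, and Appendix 3, so that each named drug has one status in every place. The sponsor chooses the status. The text should say whether a patient already taking phenytoin, carbamazepine or phenobarbital may be treated.
2. Change the reference to 4.5 in 4.1 to 4.4.
3. Add a sentence to 9.4.4: trough and AUC samples taken during use of a strong CYP3A inhibitor or inducer are flagged, and the summary is shown with and without them. This needs the co-medication recorded at each PK sample, if the case report form does not already capture it.

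The cost is protocol and appendix wording and one extra PK tabulation. No patient is dropped from the full PK summary.
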